#### 4. ABSTRACT

Name of company: Boehringer Ingelheim			
Name of finished medicinal product: Spiriva Respimat 1.25 mcg			
Name of active ingredient: Tiotropium Bromide® 1.25 mcg			
Protocol date: 18 Feb 2019	Study number: 0205-0543	Version/Revision: 1	Version/Revision date: NA
Title of study:	The effectiveness of Tiotropium Add-on therapy using a Real-world cohort of patients with Asthma		
Rationale and background:	While asthma imposes a substantial burden on the healthcare system, the cost of uncontrolled asthma is more than double that for controlled asthma patients. Asthma therapy involves a stepwise approach depending on control and severity levels. To better guide treatment decision making, it is imperative to understand the impact of different treatment choices on health outcomes in a real-world setting for patients taking ICS/LABA combinations.		
Research question and objectives:	To evaluate the effectiveness of add on therapy with Tiotropium Respimat® compared to increasing the dose of ICS in patients with a diagnosis of Asthma and on ICS/LABA therapy.		
Study design:	Retrospective cohort data analysis of patients with asthma prescribed with ICS/LABA therapy. Patients will be followed after the date of first ICS/LABA prescription and those prescribed Tiotropium Respimat® will be classified under the ‘Tio’ group while the rest will be under the ‘NonTio’ group. Outcomes will be compared between these two groups.		
Population:	Asthmatics 6 years and above and on ICS/LABA at baseline		
Variables:	Baseline measures will include patient demographics, medications, control status, comorbidities, resource use, eosinophil levels (if available), ACT score (if available).		
Data sources:	IMS Pharmedics (IMS or Database I); EMRClaims+ (Database II)		
Study size:	>6,300 (expected)		
Data analysis:	Propensity Score Matching will be conducted using baseline characteristics in order to ensure as much similarity between the two groups. Time to first exacerbation (primary outcome) will be compared between the two groups descriptively, as well as using Cox PH modelling techniques. Secondary outcomes will include rate of exacerbation, proportion of patients with exacerbation, health care resource use and cost during follow-up,		
Milestones:	Study protocol; Draft Results; Final Results		

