## **8. RESEARCH QUESTION AND OBJECTIVES**

To evaluate the effectiveness of add on therapy with Tiotropium Respimat® compared to increasing the dose of ICS in patients with a diagnosis of Asthma and on ICS/LABA therapy.

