### **9.1 STUDY DESIGN**

Data extraction from both databases (I and II, see [section 9.4](#)) will be conducted by

. All patients will be required to have a prescription for ICS/LABA therapy [e.g. Advair (Diskus and HFA), Airduo, Breo, Dulera, or Symbicort]. The date of the first prescription of ICS/LABA within the study period (Jan 1st 2016 to Nov 30th 2018) will be defined as ICS/LABA-initiation (ICS/LABAi) date. This baseline cohort will then be followed to identify two cohorts (two arms of the study). One cohort that receives a prescription for Tiotropium Respimat® 1.25 mcg (on top of baseline ICS/LABA) will be classified as the ‘Tio’ group, and the second cohort that receives a “step-up” from baseline low-dose ICS/LABA to medium/high dose ICS/LABA or from baseline medium dose ICS/LABA to high dose ICS/LABA or an additional prescription/refill of high-dose-ICS/LABA following the first prescription of baseline high dose ICS/LABA within the study period, will be classified as the ‘NonTio’ group. The date of the first prescription for Tiotropium Respimat® 1.25 mcg in the ‘Tio’ group will be defined as the index date for the ‘Tio’ group. Similarly the date of the first prescription for a “step-up” from baseline low-dose ICS/LABA to medium/high dose ICS/LABA or from baseline medium dose ICS/LABA to high dose ICS/LABA or an additional prescription/refill of high-dose-ICS/LABA following the first prescription of baseline high dose ICS/LABA (evidenced by at least 90-days of prescription utilization) within the study period will be defined as the index date for the ‘NonTio’ group.

Patients will be required to have a minimum follow-up period of 30 days after the index date for the analyses of the primary endpoint with no limit on the maximum period (this 30-day minimum follow-up period requirement will be waived in a sensitivity analysis). Subject to sample size requirements, patients will be required to have available records for at least 12 months prior to the index date to ensure no prior use of Tiotropium Respimat® and to establish baseline patient characteristics. This 12-month period prior to the index date will be defined as the pre-index period.

Figure 9.1.1 Study Design

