## 9.3 VARIABLES

### 9.3.1 Exposures

The exposure variables in this study include Tio initiation, and ICS/LABA dose increase or an additional prescription/refill of high-dose-ICS/LABA following the first prescription of baseline high dose ICS/LABA for at least 3 months.

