## 9.11 SUBJECTS

1. Patients with least one asthma diagnosis in the inpatient setting or at least two separate instances of asthma diagnosis (separated by at least 30 days) recorded in the outpatient or emergency room setting will be included (ICD 9 CM: 493.xx or ICD 10: J45-J45.999).
2. Patients will be required to be already on ICS/LABA.
3. Patients below the age of 6 years on the ICS/LABAI date will be excluded.
4. Patients will be required to have available records 12 months prior to the index date (6 months will be used if patient exclusions due to this criteria adversely affect the study sample size).
5. Patients with a diagnosis of COPD at any time during the study period will be excluded.
6. Those who are on biologics at baseline will be removed.
7. After the PSM process, unmatched patients will be excluded.

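### The new-user screen covers Tiotropium Respimat only, so asthma patients already on another tiotropium product or another LAMA can enter either group

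*Combined protocol and SAP*

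**What the plan says.** The research question in section 8 is about "add on therapy with Tiotropium Respimat® compared to increasing the dose of ICS". Section 9.3.1 names the exposures: "The exposure variables in this study include Tio initiation, and ICS/LABA dose increase", or a further high-dose refill. Section 9.1 defines the Tio group: "One cohort that receives a prescription for Tiotropium Respimat® 1.25 mcg (on top of baseline ICS/LABA) will be classified as" Tio. NonTio is defined by an ICS/LABA step-up or a repeat high-dose prescription.

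Two drug-based screens appear in the text:

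- Section 9.1 asks, subject to sample size, for records over "12 months prior to the index date to ensure no prior use of Tiotropium Respimat". This is the stated purpose of the record requirement. Section 9.11, item 4, repeats the requirement without the condition of no prior use, and allows a shorter window: "6 months will be used if patient exclusions due to this criteria adversely affect the study sample size".
- Section 9.11, item 6: "Those who are on biologics at baseline will be removed".

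One diagnosis-based rule bears on the point indirectly. Section 9.11, item 5: "Patients with a diagnosis of COPD at any time during the study period will be excluded".

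**The concern.** The look-back shows that the sponsor wants new users, but it is tied to one device rather than to the molecule or the class. A patient on ICS/LABA plus tiotropium from another inhaler who moves to Respimat 1.25 mcg meets every Tio rule, yet is switching and not adding. The same patient at an ICS/LABA step-up or high-dose refill meets every NonTio rule while already receiving the drug class under study.

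What is at stake is whether the two groups answer the question in section 8. Under the plan as written, the number of such patients would not be counted, and section 9.9 does not name this gap among its limitations.

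**Working it through.** **1. Does any provision remove or identify the patient?** Take an asthma patient on ICS/LABA plus non-Respimat tiotropium or another LAMA, with no COPD code.

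| Provision | Effect on this patient |
|---|---|
| 9.1, look-back for Tiotropium Respimat | None: different device or drug |
| 9.11 item 6, biologics | None |
| 9.11 item 5, COPD | None without a COPD code, though it probably removes many LAMA users |
| 9.3.1, exposure called initiation | Label only; no rule removes a switch |
| Table 1, polypharmacy bands | Adds one to a drug count; class not identified |
| 9.12, number of prescriptions | Same |
| 9.7.1, adjustment for unbalanced characteristics | LAMA use is not a listed characteristic, so imbalance would not be seen |
| 9.4, covariates may still be revised | A LAMA flag could be added and would balance background use, but a Tio switcher would still not be an add-on patient |

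The design figure is not shown, so this rests on the text.

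**2. The plan's own figures.** From section 9.5: 2,100 Tio and 4,200 NonTio; monthly hazards 0.0096 against 0.012 (MEZZO) and 0.0224 against 0.028 (Primo). Both give HR = 0.80. Stated power is 77% and 98%. The plan gives no alpha, sidedness or follow-up time for its own power, so I assume two-sided 5% and a common 10 months.

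Power = Φ(√(D × 1/3 × 2/3) × |ln HR| − 1.96), where D is the expected number of events.

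- MEZZO: D = 4,200(1 − e^−0.12) + 2,100(1 − e^−0.096) = 667; power 77.5%.
- Primo: D = 4,200(1 − e^−0.28) + 2,100(1 − e^−0.224) = 1,447; power 97.9%.

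Both stated powers are consistent with that follow-up.

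**3. Prior users in NonTio only.** Let c be their share and k their hazard relative to other NonTio patients. Both are assumed.

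HR_obs = 0.80 / (1 − c + kc).

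Taking the stated 77% as given (normal quantile 0.739), power = Φ(2.699 × ln HR_obs / ln 0.80 − 1.96). For example, with c = 5% and k = 0.80: HR_obs = 0.80/0.99 = 0.808, z = 0.617, power 73.1%.

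**4. Cost of excluding.** If a share c of both groups is lost without replacement, power = Φ(2.699 × √(1 − c) − 1.96).

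| c | HR, k = 0.80 | HR, k = 1.0 | HR, k = 1.2 | Power if kept, k = 0.80 | Power if excluded | Tio patients lost |
|---|---|---|---|---|---|---|
| 1% | 0.802 | 0.800 | 0.798 | 76.3% | 76.6% | 21 |
| 2% | 0.803 | 0.800 | 0.797 | 75.5% | 76.2% | 42 |
| 5% | 0.808 | 0.800 | 0.792 | 73.1% | 74.9% | 105 |

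At k = 0.80 the exclusion gains about 0.3 to 1.7 points of power. At k = 1.0 it costs 0.4 to 2.1 points.

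**5. Prior users in both groups.** This case brings in the Tio switchers. Let a share f of each group be prior users who gain nothing from Respimat, so HR = 0.80^(1 − f), with 10 months' follow-up assumed.

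| f | HR | MEZZO power, kept / excluded | Primo power, kept / excluded |
|---|---|---|---|
| 2% | 0.804 | 75.9% / 76.7% | 97.5% / 97.7% |
| 5% | 0.809 | 73.4% / 75.4% | 96.8% / 97.4% |

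**The case against.** The strongest reply is that the affected patient is hypothetical. Section 7 lists leukotriene receptor antagonists, biologics and oral corticosteroids as add-ons. No LAMA other than tiotropium, and no other tiotropium device, is named anywhere. Patients with COPD at any time in the study period are already out. Every share above is assumed, the effects are small, and their direction depends on k. Section 9.9 also mentions patient misclassification and says that no effectiveness claims should rest on the study. All of this stands as an argument about size. It does not close the gap, because the rules as written admit these patients and nothing would count them.

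A second reply is that exclusion is only one option. It also removes someone who tried a LAMA, stopped months earlier and is a genuine add-on at index, and Tio patients cannot be replaced. Matching on prior LAMA use with a sensitivity analysis is a possible alternative. The cost is real. But matching leaves the switcher in Tio, where the contrast is still not an add-on.

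Two stronger readings are tempting and should not be drawn:

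- A reader might infer that the abstract and section 9.1 disagree on strength, because the abstract says that "those prescribed Tiotropium Respimat® will be classified under the" Tio group and gives no dose there. The abstract's own header names the 1.25 mcg product, and sections 9.1, 9.4 and 9.12 all use 1.25 mcg. The abstract is using shorthand.
- A reader might put 5.5 months into the MEZZO calculation and infer that the stated 77% is wrong. In section 9.5 that figure is the source trial's follow-up, used to turn 6.4% into a hazard. Section 9.1 sets no maximum follow-up for this study, and the 77% can be reproduced at 10 months.

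**Conclusion.** The gap is real and follows from the text. The new-user screen is by device where the question calls for one by class, so a within-class switch can count as Tio initiation and a current LAMA user can serve as a control. It is a minor improvement. The share is not given and is probably small. Up to an assumed 5%, the planned HR of 0.80 stays between 0.792 and 0.809 in the cases worked.

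A reader might infer that the primary comparison is biased in a known direction. The documents do not support that: a class benefit already present in NonTio would dilute the HR, while residual severity among prior users in NonTio would move it the other way. The case rests on whether the groups match the stated question and on the low cost of the rule, not on power. It is subject to the design figure not containing such a criterion.

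**What to change.** Add to section 9.11:

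- Exclude from both groups any patient with a pre-index claim (12 months, or 6 if item 4 is invoked) for any tiotropium product or other LAMA, alone or in fixed combination.
- On the index date, exclude NonTio patients with any such claim, and Tio patients with a claim for a LAMA other than Tiotropium Respimat 1.25 mcg.

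Report the number removed per group as a row in the attrition table promised in section 9.7.1.

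The work is one eligibility line, one drug-code list applied to pharmacy claims already to be extracted, and one table row. About 21 Tio patients are lost per 1% affected (1% of 2,100), including some who had stopped a LAMA earlier. NonTio losses may be made up from the unmatched pool. At 5% of both groups without replacement, the stated 77% power becomes about 75%. A 6-month look-back makes the screen weaker.

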**Table 1: Matching Parameters**

Variable Name and Type	Description	Applicable to Study Cohort: 1=IMS, 2=EMRClaims+
ICS/LABA dose on ICS/LABAI date	The dose level of the first prescription on the ICS/LABAI date (low, medium, or high)	1 and 2
Demographics (categorical and continuous variables)	Age (10-year increments) and Gender Male/Female), Region (if available, Northeast, Midwest, South, West)	1 and 2
CCI (continuous variable)	Charlson Comorbidity Index score	1 and 2
Specific comorbidities (categorical variables)	Cardiovascular conditions, cerebrovascular diseases, hypertension, diabetes, metabolic and endocrine comorbidities, anxiety and depression, gastro-esophageal reflux disease, cancer and obesity identified using appropriate ICD codes. All above measures will be coded as binary (yes/no) variables.	1 and 2
Medications (categorical variable)	Polypharmacy level matched within a range of 2 drugs (for example, 0-2,3-5,6-8,8-10 and so on).	1 and 2
Asthma Control Status: Well Control or Poor Control (categorical variable)	‘Well Controlled’ if patient has no prescriptions for an OCS, and no asthma-related emergency department visits or hospitalizations other than the first diagnosis recorded in the data extracted (Ref: Stempel JACI 2005). Categories will include Well Controlled and Not Well Controlled.	1 and 2
Hospital admissions Outpatient visits ER visits and OCS use (categorical variables)	Poorly Controlled patients (“Not Well Controlled”) will further be matched based on the presence of asthma-related admissions, outpatient visits, and ER visits or use of OCS during the pre-index period.	1 and 2
Eosinophil levels (EMRClaims+ database only) (categorical variables)	Eosinophil level categories: <150 cells/μL, 151-300cells/μL, 301-400 cells/μL, ≥400 cells/μL (as available)	2
Asthma Control Test (ACT) results (EMRClaims+ database only) (categorical variables)	ACT score categories developed based on data distribution (as available)	2

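### Matching ignores how long patients had been on ICS/LABA, so events before ICS/LABA in some NonTio patients can be matched to events despite ICS/LABA in Tio patients

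*Combined protocol and SAP*

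**What the plan says.** **Window.** Section 9.1 sets the baseline for both arms by the index date alone: "This 12-month period prior to the index date will be defined as the pre-index period". Section 9.11 allows a shorter window: "6 months will be used if patient exclusions due to this criteria adversely affect the study sample size".

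**Start of ICS/LABA.** The ICS/LABAi date is "The date of the first prescription of ICS/LABA within the study period". There is no washout. Section 9.11 adds "Patients will be required to be already on ICS/LABA", with no minimum duration.

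**Index dates.** For Tio: "The date of the first prescription for Tiotropium Respimat® 1.25 mcg in the ‘Tio’ group will be defined as the index date". No maximum gap from ICS/LABAi is set. A NonTio patient whose baseline dose is already high is indexed at "an additional prescription/refill of high-dose-ICS/LABA following the first prescription of baseline high dose ICS/LABA (evidenced by at least 90-days of prescription utilization"). Other NonTio patients are indexed at a step-up in dose.

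**Matching.** The only item that Table 1 takes at the ICS/LABAi date is "The dose level of the first prescription on the ICS/LABAI date (low, medium, or high"). Control status is a further matching variable. Not-well-controlled patients are also matched on the presence of asthma-related admissions, outpatient visits, ER visits or OCS use in the pre-index period. Section 9.12 also names counts of overall and asthma-related prescriptions as matching measures and refers to Table 1 for them, but Table 1 lists only a polypharmacy level.

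**The concern.** The same 12 months can mean different things in the two arms. For a patient who has just started ICS/LABA, a baseline ER visit or OCS course mostly reflects asthma before that treatment. For a patient on ICS/LABA throughout, it reflects asthma that broke through it. The plan codes the two identically and matches on them.

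After index the two patients diverge for a reason unrelated to tiotropium. The new NonTio user has the benefit of ICS/LABA still to come, while the Tio patient already had it during baseline. If ICS/LABA reduces exacerbations, part of that reduction is credited to NonTio and the hazard ratio for time to first exacerbation moves against Tio.

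The planned checks could miss this. Section 9.7.1 assesses balance on baseline characteristics and, if they balance, limits the Cox model to database and treatment. A characteristic that is not derived is neither checked nor adjusted for.

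**Working it through.** The plan gives no figure for this point, so there is none to reproduce. The check has two parts.

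**1. How much of the baseline precedes ICS/LABA**

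Inputs: window W = 365 days (Section 9.1), or about 182 days under the fallback (Section 9.11); gap g = days from a true first ICS/LABA fill to index. The study period, 1 January 2016 to 30 November 2018, spans 1,064 days (about 35 months).

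Formula: f = max(0, W − g)/W.

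| Patient | g (days) | f, W = 365 | f, W = 182 |
|---|---|---|---|
| New high-dose NonTio, by refill | 30 | 335/365 = 92% | 152/182 = 84% |
| New high-dose NonTio, by refill | 90 | 275/365 = 75% | 92/182 = 51% |
| Tio | 180 | 185/365 = 51% | 2/182 = 1% |
| Tio | 365 or more | 0% | 0% |

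The day-30 row is possible only if the 90 days of utilization need not precede index, which Sections 9.1 and 9.3.1 leave unclear. Day 90 is therefore the main case. The 6-month fallback does not remove the mismatch.

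**2. What this could do to the hazard ratio**

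Assumptions, none of them from the documents:
- ICS/LABA lowers the exacerbation hazard by r = 15% to 30%.
- A share s = 10% to 50% of matched NonTio patients are new high-dose users entering by refill.
- Their matched Tio patients were on ICS/LABA for the whole baseline.
- Matching equates baseline event rates, and those rates determine later risk.

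The true hazard ratio is taken as the planned 0.0096/0.012 = 0.80 (Section 9.5).

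Formulas:
- Rate off relative to on ICS/LABA: k = 1/(1 − r).
- Baseline rate of the new NonTio user relative to the same patient's on-treatment rate: B = 1 + f(k − 1).
- With baseline rates matched, the new NonTio user's on-treatment risk is 1/B of the expected value, a reduction of d = 1 − 1/B.
- Observed HR ≈ 0.80/(1 − s·d), treating the NonTio hazard as a simple mixture.

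Index at day 90 (f = 0.753):
- r = 0.15: k = 1.176, B = 1.133, d = 0.117. With s = 0.10, HR = 0.80/0.988 = 0.81; with s = 0.50, 0.80/0.941 = 0.85.
- r = 0.30: k = 1.429, B = 1.323, d = 0.244. With s = 0.10, HR = 0.80/0.976 = 0.82; with s = 0.50, 0.80/0.878 = 0.91.

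Sensitivity of the top value (r = 0.30, s = 0.50):
- Index at day 30 (f = 0.918): B = 1.393, d = 0.282, HR = 0.80/0.859 = 0.93.
- NonTio at day 90 but matched Tio at day 180 (f = 0.507, B = 1.217): d = 1 − 1.217/1.323 = 0.080, HR = 0.80/0.960 = 0.83.
- If ICS/LABA has no effect (r = 0), there is no distortion.

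**The case against.** **The affected group may be small.** This stands. Long-standing users can have a fully treated baseline. Step-up NonTio patients can have long gaps and early Tio starters short ones. Baseline dose is matched, so s is limited to about the share of matched patients starting on high dose times the share of refill entrants who are new. Reaching 0.50 would need, for example, 60% × 83%. A reader might infer that the whole NonTio arm has an untreated baseline; the documents do not support that.

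**The effect could be overstated.** This also stands. A reader might treat the new user's baseline as wholly untreated and get 0.80/(1 − 0.30 × 0.50) = 0.94. That contradicts the window arithmetic, since 8% to 25% of the baseline is on treatment. Table 1 also matches on the presence of events, not their rate, and inside a propensity score with many other variables, so even 0.91 is a ceiling under its assumptions.

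**The plan already has a proxy.** This stands in part. A count of asthma-related prescriptions, as named in Section 9.12, would roughly separate one fill from twelve and might show imbalance if tabulated. It would therefore be too strong to say that nothing in the plan touches treated time. But Table 1 does not list the count, and it does not distinguish ICS/LABA from other asthma drugs.

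**Section 9.9 already warns about continuing high-dose users.** It does, but because Tio patients may have deteriorated and those users not. It does not mention baseline timing.

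**Conclusion.** The gap is real and worth closing before matching is run. The plan measures severity over a window fixed by the index date and neither matches on nor adjusts for prior time on ICS/LABA. A new high-dose NonTio patient with 75% of baseline before ICS/LABA (index at day 90) can be matched to a Tio patient with 0%. If ICS/LABA lowers exacerbation risk, the bias in the primary hazard ratio runs against Tio.

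The size is uncertain. The documents give neither the share of new users nor the distribution of time from ICS/LABAi to index. The range of 0.81 to 0.91 for a true 0.80 is an illustrative upper bound on assumed inputs. At its lower end it is negligible, and it shrinks if matched Tio patients were also partly untreated at baseline. It supports measuring and balancing the variable; it does not show that the primary comparison is invalid.

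**What to change.** 1. Add two variables to Table 1, the propensity model and the balance table: (a) time from first observed ICS/LABA fill to index, in categories (for example <90, 90–364 and ≥365 days, with the top category taking histories cut off by the start of the data); (b) days of ICS/LABA supply in the pre-index period. The second also helps where a long-standing user's first observed fill falls inside the window.
2. Keep the same 12-month window for every covariate. Deriving severity only after the first fill would give new users 30 to 90 days against 365 for others and create a new mismatch.
3. Only if balance on these variables is not reached, match exactly on the time category, or run a sensitivity analysis restricted to patients with ICS/LABA supply throughout the pre-index period.
4. Reconcile Section 9.12 with Table 1 on the count of asthma-related prescriptions, and state whether the 90 days of utilization must precede the NonTio index date.
5. Confirm the look-back in Database II. Section 9.4 gives a January 2015 start only for Database I.

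Matching on calendar date would not substitute, because patients indexed on the same day can differ widely in prior ICS/LABA.

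**Cost:** wording and programming, using pharmacy records that the plan already calls for. Some short-exposure patients will go unmatched. The effect on the planned 2,100 to 4,200 match cannot be estimated from the documents, which is why exact matching is held in reserve.
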